Key secondary safety endpoint

- Occurrence of bleeding, as defined by BARC type ≥ 3B, within 30 days and one year after study enrollment expressed as a proportion of patients with any of these events.

Other secondary endpoints

The following endpoints will be expressed as the proportion of patients with events:

- Death, myocardial infarction, urgent revascularization of the infarct-related artery, stroke, or major bleeding as defined by the BARC (Bleeding Academic Research Consortium) criteria* on day 30 and one year after study enrollment expressed as a proportion of patients with any of these events.

**BARC type $\geq 3B$*

- Cardiovascular death, myocardial infarction, urgent revascularization, and heart failure on day 30 and one year after study enrollment.
- Individual components of the primary clinical endpoint on day 30 and one year after study enrollment.
- Heart failure* on day 30 and one year after study enrollment.

**New heart failure or hospitalization for heart failure*

- Cardiovascular death on day 30 and one year after study enrolment.
- Occurrence of bleeding as defined by BARC type $\geq 3B$ within 30 days after study enrolment.
- Occurrence of stent thrombosis within 30 days after study enrolment.
- Delayed* aortocoronary bypass surgery due to a risk of bleeding within 30 days after study enrolment.

**Assessed by the heart team, indicating aortocoronary bypass surgery.*

- Effective* P2Y₁₂ platelet receptor inhibition defined by Platelet Reactivity Index (PRI) value 1 hour after PCI.

**Platelet Reactivity Index (PRI) less than 50% as measured by the vasodilator-stimulated phosphoprotein (VASP) phosphorylation flow cytometric assay*

The following endpoints will be displayed as the median and interquartile range (IQR):

- Duration of vasoactive pharmacotherapy and/or mechanical circulatory support in days.
- Duration of hospitalization* in days.

**Intensive care unit stay and total hospital stay*

- Maximum values of high-sensitive cardiac troponin in μg per liter.

Other pursued goals

- Cost-effectiveness is expressed as a comparison of the costs of treatment (including days of hospitalization, ICU stays, medical procedures, and pharmacotherapy) and its effect on the occurrence of endpoints. This is measured as the cost per avoided event up to day 30 and up to 1 year after randomization.

Sample size calculation

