- Statistical significance level 0.05
- Endpoint occurrence in the control group 70%
- Endpoint difference 20%.

Based on the event rates of 70% in the control group and 90% in the cangrelor group, 124 patients are needed to test the null hypothesis of no difference between groups. The required sample size fits the reachable number of VASP measurements, which is approximately 150.

Power analysis for the primary clinical endpoint (death from any cause, myocardial infarction, or stroke within 30 days)

Power analysis was performed for two scenarios: (i) the experimental group's non-inferiority and (ii) the experimental group's superiority to the control group. The sample size is computed for the patients who will receive the initial dose of the study drug. The analysis was performed in PASS 13 software (Hintze, J. (2014)). PASS 13. NCSS, LLC. Kaysville, Utah, USA. www.ncss.com).

Power analysis for non-inferiority scenario

The analysis was performed with the following settings:

- Test power 0.8
- Statistical significance level 0.05
- Endpoint occurrence in the control group based on relevant studies 50%
- Endpoint difference 10 % with a noninferiority margin of 1%.

Based on the event rates of 50% in the control group vs. 40% in the Cangrelor group and the noninferiority margin of 1%, 506 patients are needed to test the noninferiority hypothesis.

Power analysis for the superiority scenario

The analysis was performed with the following settings:

- Test power 0.8
- Statistical significance level 0.05
- Endpoint occurrence in the control group based on relevant studies 50%
- Endpoint difference 12%.

Based on the event rates of 50% in the control group vs. 38% in the Cangrelor group, a total of 536 patients is needed to test the null hypothesis of no difference between groups. Allowing for a 3% drop-out rate, 550 patients should be enrolled. The drop-out rate is based on settings of multiple clinical studies, and a higher drop-out rate is not expected in our study.

Schedule of study visits

The study started in August 2018 and reached N=304 enrolled patients in August 2021, as planned in the original version of the protocol. The end of the collection of the extended sample size, according to AMENDMENT 2 of the study protocol, is planned for January 2024. For each patient, the following order of case report forms is planned (Table 1):

- Randomization,

- Visit 1 - admission to the hospital on the first day,
- Visit 2 – Follow-up on day 7,

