The TrialDB system serves as a critical component of the data management infrastructure, specifically designed to validate the completeness and accuracy of the mandatory variables captured in the eCRF for each enrolled participant. This system systematically reviews the data entries to ensure compliance with predefined data entry standards, identifying any discrepancies, omissions, or errors in the mandatory fields. Following this validation process, the system generates comprehensive validation reports, including a detailed list of all detected issues, such as missing or incorrect data points, and a list of patients with invalid or incomplete records. These reports are then distributed to each participating study site on a regular monthly basis to allow for timely corrective actions, ensuring that the data remains accurate, consistent, and complete throughout the trial. The automated validation procedure is repeated regularly until the data issue is solved to ensure the completeness of the records. The automated validation procedures are supplemented, if necessary, by extraordinary validations communicated through the data management team.

In addition to this automated data validation process facilitated by the TrialDB system, the study will undergo an additional layer of oversight through independent monitoring conducted by a dedicated clinical research associate. This independent monitoring will involve on-site or remote monitoring visits at regular intervals, depending on the study protocol, with the specific goal of verifying the integrity and authenticity of the data recorded in the eCRF. Throughout the study, the external monitor will systematically compare the data entered into the eCRF against the source documents, including patient medical records, laboratory results, and other relevant clinical documents. This comparison ensures that the eCRF data accurately reflects the true patient outcomes and clinical events while identifying any discrepancies that may require

resolution. The error reports and their resolution are evaluated and stored by the external monitor. In addition to the regularly scheduled validations stated above, the internal audit is conducted by the study management in case of serious data issues and at the end of the data collection.

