The dual approach of automated electronic validation through TrialDB and manual verification by a monitor and investigating team aims to uphold the highest data quality standards, ensuring that the data submitted for analysis are accurate and reliable, thereby enhancing the overall integrity of the study findings. The final validation of endpoints is provided by the endpoint adjudication committee and approved by its chairperson. Each endpoint is evaluated by two independent experts, with a third expert resolving any disagreements, ensuring robust and unbiased endpoint classification.

Statistical analysis

Statistical software and responsibilities

The data will be reviewed and statistically processed in the statistical analysis center: Institute of Biostatistics and Analyses, Faculty of Medicine, Masaryk University, Brno, [name], MS.c. Ph.D. The analysis will be computed using SPSS 27.0.1 (IBM Corporation, 2021).

Handling of missing values and outliers

Missing values are subject to validation procedures and will be communicated with study sites using lists of detected problems. If correction of missing values is not possible, no imputation of missing values will be performed. The presence of outliers will be evaluated using visual inspection of the continuous variable distribution; detected outliers will be removed from the statistical computations.

Interim analysis

No interim analysis is planned for this study; the decision can be justified as follows:

Reduction of Type I Error: Conducting interim analyses introduces the risk of inflating the Type I error rate. By avoiding interim analyses, the SAP maintains the integrity of the statistical significance threshold (e.g., a p-value of 0.05).

Pragmatic Feasibility: Given the acute nature of myocardial infarction with cardiogenic shock, the timeline for endpoint occurrences (30 days for primary endpoints) is relatively short, reducing the value of interim results for decision-making purposes.

Cost and Logistical Considerations: Implementing interim analyses would require additional resources, such as re-randomization schemes, database locks, and independent review committees, which are unjustified given the study's endpoints and anticipated outcomes timeline.

To mitigate risks associated with the absence of interim analysis:

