Standard descriptive statistics will be employed in the analysis to summarize both categorical and continuous variables. For categorical variables, data will be presented as absolute frequencies (i.e., counts) and relative frequencies (i.e., percentages), clearly representing each category's distribution across the study groups. For continuous variables (including pharma-economic data), the data will be reported either as the median supplemented with the interquartile range (IQR) or the 5th to 95th percentiles range, which captures the central tendency and spread in a non-parametric manner or as the mean supplemented with the standard deviation, which provides a measure of central tendency and variability under the assumption of normal distribution. The choice between median and mean reporting will depend on the distributional properties of the continuous variables. Data visualization will use standard box and whisker plots for continuous variables and bar plots for categorical variables. Relative risks and 95% confidence intervals will be used to describe and visualize the results of endpoint analysis.

The chi-square test will be employed for categorical variables, including the primary and secondary study endpoints and all other relevant categorical data, to assess the statistical significance of observed differences between groups. This test will evaluate whether the observed frequencies in different categories deviate from what would be expected under the null hypothesis. The Mann-Whitney U test will be applied for continuous variables, as it is a robust non-parametric alternative to the t-test, particularly useful when the assumption of normality is not met. This test will determine whether there are statistically significant differences in the distribution of continuous variables between the study arms. The non-inferiority scenario will be assessed using a one-sided Z-test with a non-inferiority margin of 1%.

To ensure comparability among centers, the data for analyzing maximum values of high-sensitivity cardiac troponin will be presented as the ratio of the maximum value within seven days to the reference value for myocardial infarction at a specific center.

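### Outliers chosen by eye are deleted from continuous endpoints and costs, with no cut-off, no restriction to confirmed errors and no statement that the arms are pooled

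*SAP*

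**What the plan says.** Under Handling of missing values and outliers, the SAP sets one rule for all continuous variables: "The presence of outliers will be evaluated using visual inspection of the continuous variable distribution; detected outliers will be removed from the statistical computations". The same paragraph treats missing data differently: "Missing values are subject to validation procedures and will be communicated with study sites using lists of detected problems".

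The variables within reach are listed elsewhere in the SAP:

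- Other secondary endpoints introduces a group with "The following endpoints will be displayed as the median and interquartile range (IQR"). It contains "Duration of vasoactive pharmacotherapy and/or mechanical circulatory support in days", ICU and total hospital stay, and maximum troponin.
- Other pursued goals adds cost-effectiveness: "This is measured as the cost per avoided event up to day 30 and up to 1 year after randomization".
- The descriptive part of Statistical analysis counts pharmaco-economic data among the continuous variables. It allows either a median or a mean with SD, depending on the distribution.

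The planned test is fixed in the same section: "The Mann-Whitney U test will be applied for continuous variables, as it is a robust non-parametric alternative to the t-test". Box and whisker plots are planned for displaying continuous variables. Under Validation of data collection, a source check already exists: "the external monitor will systematically compare the data entered into the eCRF against the source documents".

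**The concern.** In these variables an extreme value is often a real outcome: a long stay, prolonged support, a very large infarct or an expensive patient. The rule deletes such a value because it looks extreme, even when it has been verified against source. Two analysts following the SAP could remove different values, and the SAP offers no means of saying which of them was right.

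The SAP also leaves open whether the distribution inspected is that of both arms together or of each arm. The consequences differ:

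- **One cut-off for the pooled arms** removes more values from the arm with the longer tail, so a real difference is attenuated.
- **A cut-off within each arm** adapts to that arm's own data. Removal is then tied to chance differences between the arms, and the test no longer holds its nominal level.

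Costs are the most exposed. If cost per avoided event is built from means or totals, the most expensive patients drop out of the calculation.

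**Working it through.** The SAP gives no figure for outliers to reproduce, so the check has two parts: reading the text, and an illustration of what the open choices can do.

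**Text.** Each safeguard was looked for in the whole SAP. None of the following is stated: a numerical criterion, a restriction to confirmed errors, pooling of the arms, blinding of the inspector, or an analysis with the values retained. The validation and monitoring procedures are described separately, and the outlier rule does not refer to them.

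**Inputs from the SAP**

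- Total size: "a total of 536 patients is needed to test the null hypothesis of no difference between groups". This reproduces: with 50% v 38%, two-sided 0.05 and power 0.80, n per arm = [1.960·√(2·0.44·0.56) + 0.842·√(0.50·0.50 + 0.38·0.62)]² / 0.12² = 267.4, so 268 per arm and 536 in all.
- Test: Mann-Whitney at 0.05, taken as two-sided. Allocation 1:1.

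**Assumptions not from the SAP**

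- Log-normal values with log-SD 1 (range 0.6 to 1.2).
- A true ratio of 1.0 for type I error and 0.8 for power.
- Five upper cut-offs to stand in for the eye, from mild to severe: the three largest values, mean + 5 SD, mean + 3 SD, Q3 + 3 IQR, Q3 + 1.5 IQR.

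**Hand check of one cut-off** (log-SD 1, median 1, Q3 + 1.5 IQR)

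- Q1 = exp(−0.6745) = 0.509 and Q3 = exp(0.6745) = 1.963, so IQR = 1.454.
- Cut-off = 1.963 + 1.5 × 1.454 = 4.143, with natural log c = 1.4215.
- Share removed = 1 − Φ(1.4215) = 7.8%.
- Mean after removal ÷ true mean = Φ(c − 1)/Φ(c) = 0.6633/0.9224 = 0.719, so the mean is about 28% lower.

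**Simulation at log-SD 1** (40,000 trials of 268 per arm; Monte Carlo standard error about 0.1 to 0.2 points for type I error and 0.25 for power)

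| | No removal | 3 largest | Mean + 5 SD | Mean + 3 SD | Q3 + 3 IQR | Q3 + 1.5 IQR |
|---|---|---|---|---|---|---|
| Values removed, pooled | 0 | 0.6% | 0.6% | 2.0% | 3.3% | 7.8% |
| Fall in mean, pooled | 0 | 5.4% | 6.0% | 12.5% | 17.2% | 28.0% |
| Power at ratio 0.8, pooled | 71% | 69% | 69% | 66% | 64% | 56% |
| Difference in means at ratio 0.8, pooled | 0.330 | 0.279 | 0.274 | 0.229 | 0.199 | 0.144 |
| Difference smaller by | 0 | 15% | 17% | 31% | 40% | 56% |
| Type I error, within arm | 5.0% | 5.3% | 5.4% | 6.1% | 8.2% | 11.4% |

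The three largest values are of all 536 when pooled, and of each arm when set within arm. The 0.330 agrees with theory: exp(0.5) × (1 − 0.8) = 0.330.

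Pooled type I error is 4.9% to 5.0% throughout. Within-arm cut-offs leave power at 72% to 74%. The ratio of medians under pooled removal moves from 0.80 to 0.83 at worst.

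**Range for log-SD 0.6 to 1.2** (6,000 trials per setting; falls in the mean from large log-normal samples)

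| Cut-off | Type I error, within arm | Fall in mean |
|---|---|---|
| Mean + 5 SD | 5.0–5.7% | 1–9% |
| Q3 + 3 IQR | 6.2–9.5% | 3–28% |
| Q3 + 1.5 IQR | 9.7–12.8% | 10–39% |

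At log-SD 0.6 the pooled loss of power is small: from 98.9% to between 96.5% and 98.7%.

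**The case against.** The strongest reply is that little of importance is at risk.

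- **Reach.** The primary clinical and key secondary endpoints are proportions and are untouched. What remains is lower-tier. This stands and limits the severity.
- **Robust methods.** Medians and a rank test hardly notice a few isolated values, which are arguably what an eye picks out. For the two mildest cut-offs, type I error is at most 5.4% at log-SD 1, even within arm. This stands too, but it is equally a reason not to remove anything.
- **Pooled reading.** The SAP speaks of the distribution of the variable in the singular, which suggests both arms together, and nothing links the box plots to outlier detection. Pooling is a fair reading and gives no inflation. It is not stated, however, and plots drawn by arm would also fit the wording. The within-arm figures are therefore a worst case.
- **Means.** The SAP reserves mean and SD for approximately normal data, so skewed costs would be summarised by medians. For description this is right. The SAP does not say which summary enters cost per avoided event, so the effect on means remains conditional.
- **Model.** Log-normality and the log-SD are assumed. Early deaths will shorten stays, support duration may include zeros, and troponin is analysed as a ratio to each centre's reference value. The percentages are illustrations, not forecasts for this trial.
- **Existing checks.** Sites receive monthly lists that include incorrect as well as missing entries, and a monitor compares entries with source. Implausible values may well be queried, but these checks do not stop a verified value from being deleted later.

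**Conclusion.** The concern holds. This is a rule that the SAP states and fixes badly, not a detail left to the protocol. Followed as written, it deletes valid observations at the analyst's discretion, and the size and even the direction of the effect depend on choices the SAP leaves open.

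With pooled arms the error rate is safe, but a real difference is diluted: slightly for medians, moderately for the rank test, and substantially for means if costs use them. With cut-offs set within each arm the 5% level is not held, by a negligible margin for mild removal and by up to about 6 points for a box-plot fence at log-SD 1. All of these sizes rest on the assumed log-normal data and the stand-in cut-offs.

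The matter should be fixed, but it does not threaten the primary clinical result. The SAP also does not exempt the continuous platelet reactivity index, from which the laboratory primary endpoint is derived; that possible extension was not quantified.

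**What to change.** Replace the outlier sentence with:

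> Extreme values will be queried against source before database lock and blind to treatment arm. Only values confirmed as impossible or as data errors will be corrected or set to missing. All other values stay in all analyses.

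Any analysis that leaves out extreme values should be labelled a sensitivity analysis. It should use one stated rule for both arms and report the number excluded per arm.

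The cost is one replaced sentence, to be made before unblinding. The site query lists and the comparison with source documents that it relies on are already in the SAP, and no extra data are needed.

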Data management

Data security within the study database is of key importance. Data of individual project are stored in a database system based on a modified version of the TrialDB web-based system for the data collection, which was developed by the Institute of Biostatistics and Analyses, Faculty of Medicine, Masaryk University, Czech Republic, on the base of TrialDB system (Brandt et al. I, 2003). This online system has changed its layout and structure, making data entry even more convenient, while maintaining security measures at the same level. The system is designed as a robust foundation for collecting substantial amounts of data in clinical trials and/or clinical registries. It is fully customized to the structures of individual projects. The online application is accessible to users through a web browser. The security of individual records within the database is guaranteed via de-identified data collection. The identity of each patient is replaced with an identification number (ID), which does not allow any backward identification of that person. The unequivocal identification of a patient is only known to the attending physician or authorized health care professional.

Randomization

The patient will be randomized after the informed consent form has been signed. As this is an acute condition, an abbreviated version of the informed consent form (one-page A4 format) will be available to the patient following applicable law. After the patient's condition has stabilized, a full version of the informed consent form will be presented to the patient (consent to continue in the clinical trial). The full and abbreviated versions of the informed consent form are attached to the final version of the protocol.

An online database system (TrialDB) provides randomization for data collection. After entering basic patient data (age, gender, body weight, type of acute myocardial infarction, and mechanical ventilation upon admission), a study arm inclusion and a randomization code are generated based on a predefined randomization scheme. The patients are randomized in a 1:1 allocation ratio using random permuted blocks, with the size of block four stratified by the center.

Unblinding

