- External monitoring is performed by an independent Clinical Research Associate (CRA), which provides regular site monitoring and data validation to ensure data quality and patient safety.
- The Data Safety Monitoring Board (DSMB) periodically reviews accumulated safety data, including adverse event frequencies and severity, to address any unexpected risks promptly.

Substudies

The following substudies are planned:

- Echocardiographic substudy,
- Magnetic Resonance Imaging substudy.

Subgroup analysis

The analysis of the following subgroups is planned in the study:

- Women versus men,
- Patients with prehospital time delay duration 3 hours and longer versus less than 3 hours,
- Patients with and without out-of-hospital cardiac arrest,
- Patients with and without mechanical ventilation,
- Patients with and without mechanical circulatory support (e.g., IMPELLA, ECMO)*
- Patients with and without persistent coma (Glasgow Coma Scale < 8) at admission,
- Patients with and without diabetes,
- Patients with and without obesity,
- Patients who are cigarette smokers versus non-smokers,
- Patients with and without multivessel disease,
- Patients with and without a history of heart failure.

**A time-dependent covariate analysis will be performed instead of standard subgroup analysis to prevent bias due to treatment-dependent selection effects for mechanical circulatory support (MCS), which may occur post-randomization.*

Handling of Post-Randomization Events (MCS)

MCS use will be modeled as time-dependent covariates in survival analyses to avoid bias introduced by post-randomization treatment effects. These covariates will be introduced into the primary and secondary outcome models as follows:

Time-Dependent Covariate Analysis

To accurately account for the influence of MCS on study outcomes, these variables will be modeled as time-dependent covariates within the Cox proportional hazards model:

Primary Model:

- $HR = \beta_1(\text{Treatment}) + \beta_2(\text{Mechanical Ventilation (time-dependent)}) + \beta_3(\text{ECMO (time-dependent)}) + \epsilon$
- This ensures that the estimation of treatment effects is not confounded by patients who deteriorate and need additional support after randomization.

Competing Risks Model (Fine & Gray) for Non-MACE Outcomes:

- If MCS is strongly associated with mortality before the primary endpoint, a competing risks approach will be applied using the Fine & Gray subdistribution hazard model.

Sensitivity Analysis

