- Inverse Probability of Treatment Weighting (IPTW) will be applied as an alternative approach to adjusting for potential differences between patients requiring MCS and those who do not.

Reporting & Interpretation

- The Kaplan-Meier curves for MACE outcomes will be stratified based on whether patients required MCS, but formal statistical comparisons will be limited to time-dependent Cox models to avoid survivor bias.
- Forest plots will be presented for pre-randomization subgroups only.

Analysis population

The patients enrolled in the study will be summarized in a CONSORT flow diagram. The analyses will be conducted using a modified intention-to-treat principle (MITT), an intention-to-treat principle (ITT), and a per-protocol (PP) approach. The MITT population includes all randomized patients in the trial who received a dose of the study drug. The ITT encompasses all trial-randomized patients, and the PP population consists of all randomized patients who received the full dose of the study drug as per protocol. Treatment classification in all scenarios will be based on the randomized treatment. The MITT will serve as the primary analysis approach; analyses based on ITT and PP populations will be considered secondary and confirmatory.

Data Sharing

The data used in the published scientific papers will be available according to the requirements of the respective scientific journals. To mitigate the risk to patient privacy, the data will be

anonymized and identified through masking or generalization of direct and some indirect identifiers. Only variables used in the given analysis will be included in the shared dataset.

Statistical analysis

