A p-value of 0.05 will be adopted as the threshold for determining statistical significance across all analyses. All statistical analyses will be conducted in strict accordance with the regulatory guidelines outlined in the E9 Statistical Principles for Clinical Trials document published by the U.S. Food and Drug Administration (FDA) under the reference FDA-1997-D-0508. These guidelines ensure that the statistical methods employed adhere to established clinical trial data analysis standards, ensuring rigor, reproducibility, and validity of findings.

Variables and tables will be presented in the order in which the sections are shown in the eCRF. Parameters recorded in more than one SI unit (e.g., lab units) will be converted into a single SI unit as appropriate.

Description of patients' characteristics

Prior to the analysis of the primary and secondary endpoints, the treatment groups (or any groups in subgroup analyses) will be compared about the following patients' characteristics:

- Demographics: age, sex, body weight, body mass index (BMI), obesity, and cigarette smoking.
- Characteristics of AMI at admission: type of acute myocardial infarction (STE- or NSTEMI), mechanical ventilation upon admission.
- Time delay: from symptoms to hospital, from symptoms to reperfusion.
- Out-of-hospital cardiac arrest: cardiopulmonary resuscitation before admission, first documented rhythm, time to return of spontaneous circulation (ROSC) (min), external cardiac massage - before admission, on admission, overall duration, mechanical ventilation, regulation of body temperature, target value.
- Patient's status at the time of admission: blood pressure - left arm systolic/diastolic (mmHg), blood pressure - right arm systolic/diastolic (mmHg), pulse rate (BPM), cyanosis, mydriasis, transient mydriasis, deep unconsciousness without prior treatment with hypnotics.
- Treatment with vasopressors and/or inotropic agents, noradrenaline, adrenaline, dopamine, dobutamine, another vasopressor agent, another inotropic agent.
- Analgosedation: analgosedation, opioid (morphine, fentanyl, sufentanil), benzodiazepine (midazolam, diazepam, other), propofol, another analgosedation method.

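### The descriptive MACE Kaplan-Meier curves split by MCS use carry immortal-time bias, and the ventilation subgroup is not tied to admission status

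*SAP*

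**What the plan says.** **MCS curves.** Under Reporting & Interpretation the SAP states: "The Kaplan-Meier curves for MACE outcomes will be stratified based on whether patients required MCS". The same sentence limits formal comparisons to time-dependent Cox models and names survivor bias as the reason. Additional analyses counts time to event from the date of randomization. The footnote to Subgroup analysis puts a time-dependent covariate analysis in place "instead of standard subgroup analysis to prevent bias due to treatment-dependent selection effects for mechanical circulatory support (MCS), which may occur post-randomization". No landmark or time-updated curve is described.

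**Ventilation subgroup.** Subgroup analysis lists "Patients with and without mechanical ventilation" with no time point. The coma item in the same list is dated: "Patients with and without persistent coma (Glasgow Coma Scale < 8) at admission". The asterisk that takes a factor out of standard subgroup analysis stands on MCS only. The Cox model under Time-Dependent Covariate Analysis nevertheless contains the term "Mechanical Ventilation (time-dependent".

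**What points to admission status.** Randomization has the site enter "type of acute myocardial infarction, and mechanical ventilation upon admission", among other data, before the code is issued. Description of patients' characteristics lists "type of acute myocardial infarction (STE- or NSTEMI), mechanical ventilation upon admission" under the status at admission. Reporting & Interpretation adds: "Forest plots will be presented for pre-randomization subgroups only".

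**The concern.** A Kaplan-Meier curve from randomization should group patients by something known at randomization. Grouping by MCS use that may start later borrows information from the future. A patient who dies before MCS could be started can only be in the no-MCS group, and a patient in the MCS group cannot have died before its start. The curves then separate even if MCS does nothing. The SAP recognizes this for testing, yet still plans the figure that shows it, and readers will compare the two curves by eye.

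The ventilation subgroup raises the related question of when status is read. If it were read after treatment had begun, a drug that changes who deteriorates would move patients between subgroups differently by arm, and the within-subgroup effects would no longer compare randomized groups. The SAP's safeguard against such selection names MCS only, although its own model treats ventilation as something that changes over time.

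**Working it through.** No figure in the SAP is in dispute here. The calculations only show how large the distortion can be.

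**A. MCS curves when MCS has no effect**

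Inputs:
- Day-30 event proportion 50%: the SAP's control-group rate for the primary clinical endpoint. The event is treated as death, so it rules out later MCS.
- Share of patients who would receive MCS if they lived long enough: 30% (assumed).
- Time to MCS start: exponential with median m = 0.5, 1, 2 or 5 days (assumed; the SAP gives none).
- Survival S(t) = exp(−ln2 · (t/30)^k), so S(30) = 0.5. Shape k = 1 is a constant hazard. Shape k = 0.5 is front-loaded: the share of 30-day deaths in the first 2 days is (1 − 2^(−√(2/30)))/0.5 = 33%, against 9% for k = 1. Both shapes are assumed.

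Formulas, with μ = ln2/m:
- a = ∫₀³⁰ μ·exp(−μv)·S(v) dv, the chance that MCS starts before death and before day 30, among those due for it.
- b = a − 0.5·(1 − exp(−30μ)), the chance of that and of death by day 30.
- Death with MCS = b/a.
- Death without MCS = (0.5 − 0.3b)/(1 − 0.3a).

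Worked case, k = 1, m = 5: ln2/30 = 0.02310 and μ = 0.13863, so a = (0.13863/0.16173)·(1 − 2⁻⁷) = 0.8504 and b = 0.8504 − 0.5·(1 − 2⁻⁶) = 0.3583. Death with MCS = 0.3583/0.8504 = 42.1%. Death without = (0.5 − 0.1075)/(1 − 0.2551) = 52.7%. The gap is 10.6 points.

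| Median MCS start (days) | k = 1: MCS / no MCS (gap) | k = 0.5: MCS / no MCS (gap) |
|---|---|---|
| 0.5 | 49.2 / 50.3% (1.2) | 45.1 / 51.9% (6.8) |
| 1 | 48.3 / 50.7% (2.3) | 42.9 / 52.5% (9.6) |
| 2 | 46.7 / 51.3% (4.6) | 39.8 / 53.4% (13.6) |
| 5 | 42.1 / 52.7% (10.6) | 33.6 / 54.7% (21.1) |

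The true gap is zero in every row. Gaps are taken before rounding. A simulation of 2 million patients with the same inputs gave the same pattern.

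**B. Ventilation subgroup, if status were read after treatment had begun (purely hypothetical)**

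Let severity S be uniform on 0 to 1, the risk of death 0.2 + 0.6S (mean 50%), and let a patient be ventilated if severity exceeds 0.5. Suppose the drug lowers severity by 0.2, which gives 50% vs 38%, the SAP's superiority assumption.
- Grouped by baseline severity: above 0.5, mean severity is 0.75 vs 0.55, so risk is 65% vs 53%. Below 0.5, it is 0.25 vs 0.05, so 35% vs 23%. Both differences are −12 points.
- Grouped by severity after treatment: above 0.5, mean severity is 0.75 vs 0.65, so 65% vs 59%. Below 0.5, it is 0.25 vs 0.15, so 35% vs 29%. Both differences are −6 points, half the true effect.

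Now suppose instead that the drug changes only ventilation use, moving the threshold from 0.5 to 0.6, and has no effect on death. Ventilated: 68% vs 65%, risk ratio 0.68/0.65 = 1.05. Not ventilated: 38% vs 35%, risk ratio 0.38/0.35 = 1.09. Both are spurious. The model builds in the mechanism, so it shows the direction of the problem and not its likely size in this trial.

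**The case against.** **On ventilation, the other side is strong.** A reader might infer that a patient intubated on day 3 belongs to the ventilated subgroup, and hence that the planned subgroup effects are biased. The SAP does not say so. It gives no time point, and where it does date a ventilation variable as a patient characteristic, the date is admission. Forest plots are confined to pre-randomization subgroups. Diabetes and obesity are also undated in the list, so the dated coma item does not show that the rest are read later. What stands is an inconsistency: ventilation is a standard subgroup in one place and a time-dependent covariate a few lines on. The SAP never says which listed subgroups count as pre-randomization, and the forest-plot rule does not govern the subgroup logistic models under Additional analyses.

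**On the curves,** the SAP names survivor bias, and the plots are descriptive. That limits the consequence but does not correct the figure. Splitting by use at any time is an inference from the wording, though the likeliest reading.

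**On size,** the objection is fair. With a median MCS start at half a day and a constant hazard, the gap is only about 1 point. MCS patients may be sicker, which could mask or reverse the gap. A non-fatal infarction that itself leads to MCS would also work the other way. A reader might take the 1 to 21 points as bias in the cangrelor versus ticagrelor comparison; they are not. They size the contrast between MCS and no-MCS patients. Nor does the SAP offer a basis for a given difference in later ventilation between arms: all patients are treated with ticagrelor after the first four hours (Unblinding).

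**Conclusion.** The point on the MCS curves holds as the plan is written. Grouping by later MCS use from a time origin at randomization produces immortal-time bias in the figure. Under the assumed start times and hazard shapes, the false day-30 gap is about 1 to 21 percentage points with no MCS effect. Its net direction in real data cannot be predicted, because severity acts as well.

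The point on ventilation holds as a definition left open, not as a demonstrated bias. The effects would be distorted only if ventilation at any time were used, and the SAP leans towards admission status without saying so.

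The primary chi-square and non-inferiority tests in the whole population do not depend on either item. Both should be settled before the analysis, but neither threatens the main result.

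**What to change.** 1. **MCS curves.** Replace them with landmark curves: patients event-free at a prespecified landmark, grouped by MCS status at that time, with follow-up counted from there. Alternatives are time-updated (Simon-Makuch) curves or dropping the figure. Choose a landmark that the recorded data can support: Additional analyses works from dates, so a landmark within the first day may not be feasible. The cost is that landmark curves leave out patients with an event before the landmark, and the figure should state how many. Splitting by MCS in place at randomization would also avoid the bias, but that status is not among the listed baseline characteristics, so its availability would need checking.
2. **Ventilation subgroup.** Define it as ventilation status on admission, as entered before allocation, and use only that value in the subgroup models and the forest plot. Ventilation that starts later stays in the time-dependent analysis. This needs only a change of wording, since the value is already entered for every randomized patient.
3. **Forest plot.** State which of the listed subgroups count as pre-randomization.
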